### 1.9.7.3 Unmasking of individual study subjects in case of medical emergency

The code linking treatment to medication ID will be maintained (i by the labeling company, (ii by the unmasked statistician(s), to allow the investigator to break the masking for an individual subject solely in the case of a medical emergency or necessity.

**Unmasking: Code breaks must occur only when specific knowledge of the treatment group (treatment or placebo) would dictate the treatment or course of action to follow to manage the subject's medical emergency or necessity.**

In the event a code break must occur, the investigator will first contact the sponsor prior to unmasking (contact details found on cover page. For life-threatening serious adverse event only, and if the investigator has been unsuccessful in contacting the sponsor, the investigator may proceed with unmasking the subject without first notifying the sponsor by following unmasking instructions provided in the study binder. The investigator must then notify the sponsor within 24 hours of breaking the code. Information pertaining to all circumstances that resulted in unmasking, such as reason, date and time, shall be clearly recorded in the subject's source documents. In addition, the sponsor may also, for matters relating to health risk concerns, unmask individual subjects at any time.

**After unmasking:** After unmasking of a particular subject, the subject should permanently interrupt the treatment and be withdrawn, unless instructed otherwise by sponsor. In addition, the nature of the treatment (treatment or placebo should be stored in a sealed, labeled and signed envelope so that the subject, study site or sponsor stay masked to the treatment until the end of the study. The investigator should not reveal the nature of the treatment to the subject, the sponsor, or other study team members until after the end of the study.

**Unintentional unmasking:** In case of unintentional unmasking by subject or study team, the date and reason must be documented and sponsor informed promptly. Sponsor will decide whether subject should be kept in the trial, re-randomized, or withdrawn.

## 1.9.8 Dose Abuse, Lost Medication or medication shortage

### 1.9.8.1 Dose abuse

Subjects will be discouraged to take more than one capsule per day, except in case of a missed dose. Because only the percentage of deuterated vitamin A, rather than the absolute values of vitamin A is believed to affect efficacy, there is no expected benefit in taking more than one capsule per day. Taking more than one capsule per day may increase the chance of adverse reactions and lead to subject withdrawal for non-compliance with study instructions.

### 1.9.8.2 Lost medication or medication shortage

In the event a subject loses a medication packaging, a replacement may be provided if available. To avoid abuse, subject will be informed that they could be withdrawn from the study if they lose their medication.

packaging a 2nd time. Second replacement packaging may be provided only at the discretion of sponsor and only under exceptional circumstances. No more than two replacements will be provided.

If for any reason subject's study drug supply ends up being insufficient to complete the study, subject should be scheduled for the last visit (24-month follow-up within 1 to 8 days of running out of study drug supply, preferably when subject has at least 1 remaining capsule of study drug ("1 day before running out"). If this follow-up visit ends up outside of the visit window, it should be documented as a protocol deviation.

#### 1.9.8.3 *Lapse in treatment*

If a lapse in treatment occurs, the days and duration that subject was off-treatment shall be documented. If the subject is off-treatment for a period longer than 4 weeks, and if subject lives relatively close to study site, study team may collect subject's plasma in an unscheduled visit to acquire pharmacokinetic data caused by lapse in treatment.

Lapse in treatment may occur for a variety of reasons, including health-related reason, temporary interruption, lost medication, subject forgetting to take treatment, study drug availability, family or personal reason, etc.

Lapse in treatment shall not result in modifications or postponing of subsequent follow-up visits, unless instructed by sponsor. Lapse in treatment may result in early withdrawal.

#### 1.9.9 Study Drug Physical Description

**Note: Drug may possibly be packaged in blister packs instead of HDPE bottles, in which case "bottle" or "packaging" in this protocol shall mean indifferently "bottle" or "blister pack." In addition, drug packaging may contain more than one month's worth of study drug, in which case study team shall adjust the quantity dispensed accordingly.**

The study drug unit dosage is an opaque hard gelatin capsule. Color may vary by production lot. All capsules containing active ALK-001 or placebo look, weigh and smell the same and cannot be differentiated. Capsules are packaged and sealed in opaque plastic (HDPE) bottles with a child-resistant cap. Bottles may contain an oxygen scavenger pouch (or canister) and a cotton ball. Both cotton ball (and any residual cotton threads) and oxygen scavenger should be taken out of the bottle after breaking the seal and must be discarded. The oxygen scavenger is not needed once the seal has been broken.

Real-time stability data will be acquired throughout the study to ensure stability of all dispensed medications. Based on existing stability data acquired on previous batches of study drug, capsules are expected to be stable for at least 24 months. Bottles deemed to contain capsules out of specification may be collected by sponsor and replaced by new bottles.

#### 1.9.10 Packaging and Labeling

Bottles delivered to the sites are expected to be labelled and require no further labeling. A sample of the label is found in section [1.22.1](#) and includes the following statement: "**CAUTION – NEW DRUG : LIMITED BY FEDERAL LAW TO INVESTIGATIONAL USE.**" A medication ID corresponding to the randomization code (eg: GA2648) is printed on the label, along with dosage instructions for the study subject.

### **1.9.11 Testing, Tampering Study Drug Prohibited**

It is prohibited to tamper with study drug, including used medication bottles and contents collected from subjects. Any unused study drug is the sole property of the sponsor and shall not be broken down, analyzed, or tested in any way.

### **1.9.12 Study Drug Supply: Receipt, Storage, Dispensing and Disposal/Return**

#### *1.9.12.1 Receipt of Drug Supplies*

Sponsor will be responsible for coordinating the shipment of study drug to sites or study subjects.

Throughout the study, study team shall document receipt, storage, dispensing, and collection/return/disposal of study drug. Damaged or unusable study drug in a given shipment shall be documented and immediately communicated to sponsor.

#### *1.9.12.2 Study Drug Storage*

General storage and temperature monitoring: All study drug should be stored at room temperature, unless instructed otherwise by sponsor. Temperature should be monitored and recorded at least once daily with an appropriate device.

The study drug should be stored in a pharmacy, research pharmacy or in the investigator's office, as long as the study drug is stored in a locked cabinet/safe separate from FDA-approved medications, and the temperature is appropriately monitored. Because the product is light sensitive, the storage environment should not expose the study drug packaging to constant light or to direct sunlight. Study drug can be stored next to other investigational drugs. Everyone with direct access to the study drug should be listed in the regulatory binder.

For storing study drug collected from subjects, see section [1.9.12.4](#).

#### *1.9.12.3 Dispensing of Study Drug; Direct to Patient Shipment*

Dispensing by designated personnel only: For study drugs stored at the study site, study drug shall be dispensed only by designated personnel.

Two signatures required: To ensure that the proper medication ID is dispensed, dispensing shall preferably be performed by one designated person plus a witness checking that the proper medication is being dispensed.

First dispensing: At the end of the screening visit, which determines the beginning of the run-in period, a subject who receives the study drug for the first time should be provided instructions on storage conditions (room temperature, do not store in a car or in a sunny area, how to open the bottle/packaging, and at what time to take the study drug (preferably the same time as other medications. Subject should break the seal, discard the cotton ball if present (and any possible residual cotton threads, and discard the oxygen scavenger if present. The first capsule should be taken in front of the person dispensing the medication, and subject observed for approximately thirty minutes prior to being discharged.

Direct to patient shipping by site, research pharmacy or sponsor representative: study drug may be shipped directly to the subject by the study team, research pharmacy or by a sponsor representative. Study drug shall be packaged in standard unmarked cardboard boxes. Unless unavailable or impractical, which should

be documented, shipping to patient must be overnight, with direct signature required and delivery preferably in the morning. All study drug shipment shall be adequately logged.

Exposure of study team to study drug: ALK-001 is a vitamin A. Vitamin A is mildly teratogenic and is not considered a hazardous drug. No special precautions beyond reasonable care are required for the handling of the study drug. The study drug is formulated in an oil, self-contained in individual and sealed unit-dose capsules, packaged in a sealed plastic bottle, the content of which will only be accessed by the study subject. As such there is very little risk of environmental exposure of the study team to the study drug.

#### *1.9.12.4 Collection from Subjects/Return of Study Drug*

Collection of study drug from subjects: Subjects should be instructed to return all used or empty, partially used, or unused bottles to the study site at each visit. The number of remaining capsules should be recorded at time of return. Remaining capsules may be transferred into a freshly dispensed bottle of study drug unless directed otherwise by sponsor.

Storage of collected study drug: Study team will store all collected study drug until the end of the study or otherwise decided by sponsor. Study drug collected from subjects should be stored separate from the unused study drug (except when permitted by sponsor, and if such study drug packaging still contains unused drug, in a locked cabinet/safe/drawer accessible by designated personnel only).

If a subject has to permanently interrupt taking the study drug, all study drug shall be collected from subjects. Such collected medications should be stored at the site and not be administered to any other subject, unless directed otherwise by sponsor.

Return of study drug. The sponsor or monitor will pick-up these bottles, or they will be shipped to sponsor or to a designated facility for destruction, or destruction at the site will be requested, if feasible. No destruction should take place without request from sponsor.

At the end of the study, site close-out, or upon request by sponsor, unused study drug may be returned to sponsor or shipped to a designated address (including other study sites). Study drug packaging will be shipped using standard couriers such as UPS, USPS or Fedex. If necessary, sponsor will provide a temperature logger and specialized shipping containers and instructions.

### **1.9.13 Drug Accountability**

#### *1.9.13.1 Drug supply*

The study team will maintain records of study drug delivery to the site, study drug inventory, the number of bottles of study drug provided to each subject, the amount of unused study drug returned to the site by the subject, and the amount of unused study drug returned to the sponsor (or where otherwise mandated, a certificate of destruction of any unused study drug). Study monitors will verify the site's study drug and accountability records.

#### *1.9.13.2 Study drug reconciliation*

Subjects shall be instructed by study team to bring back all study drug to each follow-up visit. The study team shall then count all remaining capsules in subjects' bottles, and calculate the theoretical numbers of remaining capsules. Data will be recorded in the source document and any significant discrepancy investigated. If subjects forget to bring back all study drugs, study drug reconciliation cannot be performed and subjects shall be reminded to bring back all study drug to the next visit.

Discrepancy in study drug reconciliation or non-compliance with instructions shall be investigated by investigator and may result in withdrawal of a subject.

## **1.10 MONITORING OF COMPLIANCE**

Compliance will be assessed and encouraged using the following means:

- *At each visit:*
  - Study team should discuss the importance of treatment compliance with subjects (daily drug intake, timing of drug intake, avoidance of vitamin A containing supplements, avoidance of vitamin A-rich items, and avoidance of other types of supplements except when permitted).
  - Study team should perform study drug reconciliation by counting the number of capsules remaining in the dispensed bottles and comparing this number to the theoretical number of capsules remaining.
  - Study team should remind subjects that they may be withdrawn from the trial at any time if they are thought to be insufficiently compliant.
- *Between visits:*
  - Study team will call subjects periodically to check compliance with the study drug and remind them of study instructions. This phone call should be made according to the Schedule of Events to the extent possible. Documented notes detailing the content of each phone call should be taken.

## **1.11 PRIOR AND CONCOMITANT MEDICATIONS; RESTRICTED FOODS AND MEDICATIONS**

### **1.11.1 Prior (pre-treatment) and Concomitant Therapy**

#### *1.11.1.1 Prior medication or therapy (before randomization/treatment)*

The investigator should record as prior medication or therapy all medications, including prescription and over-the-counter medications, vaccines, vitamins and supplements, taken by the subject from 30 days prior to the start of screening, up to the day of randomization. Investigator should also record any retinoid therapies taken up to 30 days prior to screening. This includes any vitamin A-containing supplements, accutane, acitretin, retinoic acid, bexarotene, and etretinate.

Preexisting clinically-effective therapies for a subject's existing condition must not be changed for the purpose of satisfying eligibility requirements and entering the subject into the study.

#### *1.11.1.2 Concomitant medications and/or therapy (during treatment)*

Starting from the administration of the first dose of the study drug, investigator shall record all concomitant therapies. These include prescriptions or over-the-counter medications, vaccines, vitamins, and supplements.

Efforts should be made to keep subjects' concomitant therapies stable throughout the study. Any change and reason for change in concomitant therapies should be documented.

## 1.11.2 Restricted Foods and Supplements

### 1.11.2.1 *Vitamin A from liver and Vitamin A Supplements*

#### 1.11.2.1.1 Prohibited

Subjects will be informed **not** to consume:

- Food items that contain excessively large amounts of vitamin A. These include: **liver-based products** (including liver oil, liver sausage, foie gras, etc.), giblets
- **Vitamin A or beta-carotene containing supplements.**

At screening, the investigator should check whether the prospective subject has used vitamin A or beta-carotene containing supplements over the past 30 days. If so, prospective subjects must agree to stop in order to enroll into the study, and not take any vitamin A and beta-carotene containing supplements, at any dose, at any time during the study.

#### 1.11.2.1.2 Allowed

Fruits and vegetables are allowed without any restrictions. They only contain carotenoids which are poorly absorbed and converted to vitamin A when taking preformed vitamin A.

### 1.11.2.2 *Recommended: AREDS-2 or Equivalent. Prohibited: AREDS*

At screening, the investigator should investigate the subject's use of AREDS (also known as AREDS-1) and AREDS-2 supplements.

AREDS is prohibited: AREDS contains beta-carotene, which is prohibited during the study. Subjects who are taking AREDS at screening should immediately stop taking AREDS until the end of the study.

AREDS-2 is recommended: AREDS-2 may slow the progression of intermediate to advanced AMD. In this study, AREDS-2 (or other brands that contain similar ingredients) is recommended for all patients, especially those with intermediate AMD in the fellow eye. Subjects who decide that they want to start taking AREDS-2 will be instructed to start taking it immediately. This is to avoid adding new concomitant medications during the study.

### 1.11.2.3 *Discouraged: Other “eye” supplements*

At screening, study team should investigate subject's use of supplements, and record supplements on the concomitant medication log. While not prohibited, supplements containing ingredients such as saffron, curcumin (turmeric), bilberry, resveratrol, CBD oil, and “multivitamins for vision” (except AREDS-2 and equivalent), are discouraged.

### 1.11.2.4 *Discouraged: Over two (2) alcoholic beverages a day*

Because alcohol consumption can result in accelerated metabolism and secretion of vitamin A by the liver, increasing the risk of adverse reactions [97], subjects will be encouraged to limit their alcohol consumption to two (2) alcoholic beverages per day.

## 1.11.3 Concomitant Medications, Prohibited and Restricted Medications, Participation in Other Clinical Trials

Prohibited (oral) retinoid therapies: Throughout the study, subjects are prohibited from taking any retinoid-based medications (including accutane, isotretinoin, acitretin, retinoic acid, bexarotene, and etretinate) except in the case of a medical necessity. Retinoids may trigger significant ocular and systemic adverse reactions, and could interfere with the pharmacokinetics or the mechanism of action of ALK-001.

Restricted medications: antibiotics of the class of tetracycline are known to interact with vitamin A. As such, tetracyclines should not be used by the subject unless no other class of antibiotics would be deemed efficacious. Tetracyclines include for example Demeclocycline (Declomycin), Minocycline (Minocin), Tetracycline (Achromycin), Doxycycline.

Prescription eyedrops allowed according to label and if medically necessary: Unless medically necessary, subjects are prohibited from using eyedrops except for over-the-counter lubricating eyedrops, for which there are no restrictions. When medically-necessary, FDA-approved prescription eyedrops may be used according to the approved label (no off-label use). Exception may be granted by sponsor, and should be documented.

Prohibited participation in other trials or studies: subjects are prohibited from enrolling or participating in any other clinical trials that involve a drug or treatment (investigational or not) for the treatment of GA, AMD or for any other condition, unless clinically necessary and recommended by the PI and approved by sponsor. Subjects are also prohibited from enrolling in studies that involve retinal imaging (see section [1.12.35.1](#)).

Medication/Food/Drinks	During Treatment
Liver, liver oil, sausage, foie gras, giblets	Prohibited
Fruits & Vegetables	No restriction
Vitamin A or Carotene containing supplements	Prohibited
AREDS and AREDS-2 supplements	AREDS: prohibited AREDS-2: encouraged
Following supplements: saffron, curcumin (turmeric), bilberry, “multivitamins for vision” (Except AREDS-2), resveratrol, CBD oil	Discouraged
Following oral medications: accutane, isotretinoin, acitretin, retinoic acid, bexarotene, etretinate	Prohibited
Prescription eyedrops , except when medically necessary and according to FDA approved use	Only when medically necessary and according to drug label
Tetracycline antibiotics	Only if no other antibiotics class is available
Alcohol beverages	2 drinks max. per day

## **1.12 ASSESSMENTS AND ORDER OF PROCEDURES**

Timing and schedule of all events is found in section [1.2](#). Details for each procedure are provided in this section, with practical details in the various manuals of operation.

### 1.12.1 Primary Study Eye

The PI and sponsor should agree on the choice of primary study eye by evaluating all inclusion criteria for each eye. The choice of primary study eye may later be changed based on the totality of data collected during the study (quality of imaging, conversion to CNV, reading center choice, etc.) but one eye must be selected prior to running efficacy analyses on atrophic lesions. The following guidelines, which may be amended from time to time in the manual of operations or the source documents, should be used to choose the study eye:

- *For subjects with only one eye that meets all “study eye” inclusion criteria*, that eye should be selected as the primary study eye.
- *For subjects with both eyes that meet all inclusion criteria*, the study eye shall be selected but the choice may be modified at the end of the study based on the following:
  - Well-delineated and accurately measurable atrophic lesions
  - Atrophic lesions likely to stay within the field of view over the next 2 years
  - Atrophic lesion border is closest to foveal center (in the case of foveal sparing)
  - Visual acuity is closest to the range 20/40 to 20/100.
  - Imaging availability and quality at all time points during the study

During the study, both eyes should undergo all procedures, or as described in the manual of operations.

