#### Study eye exclusion criteria:

28. Study eye has historical or active CNV.
29. Study eye has refraction higher than 6 diopters (positive or negative) approximately, except if retinal imaging can be properly focused.
30. Study eye has GA thought or proven to be caused by any condition other than AMD.
31. Study eye has GA lesions expected to (i) expand larger than the imaging field of view, or (ii) merge with other retinal features (optic disc or peripapillary atrophy, other non-AMD atrophic lesions, etc.) during the 2 years of the study.
32. Subject, in the case of a systemic treatment, or study eye, in the case of a monocular treatment, has previously received treatment, surgery or procedure for GA or AMD, including clinical trials, except when there is documented evidence that the subject was receiving placebo or was part of a sham group.
33. Study eye has active or history of ocular disorder, which may confound assessment of the retina morphologically or functionally, as judged by principal investigator.
34. Study eye has uncontrolled elevated intraocular pressure, retinal detachment, RPE tear, recurring uveitis, retinal vein occlusion, diabetic retinopathy, diabetic macular edema.

35. Study eye has history of submacular surgery, any surgical intervention for AMD, vitrectomy, or device implantation (except IOL).
36. Study eye has received intravitreal injections or cataract surgery within 90 days of randomization.
37. Study eye is expected to require cataract, epiretinal membrane, or ocular surgery over the next 2 years as judged by principal investigator.

**NOTE:** PI shall make the final determination regarding all eligibility criteria.

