2.2.3 Secondary Efficacy Endpoints

- Growth rate of the total area of GA lesion(s) between baseline and Month 12
- Growth rate of the total area of GA lesion(s) between Month 12 and Month 24
- Growth rate of the total area of GA lesion(s) between Month 6 and Month 24

- Change from baseline in LLD score
- Change from baseline in maximum reading speed at Month 24, as measured by MNRead (wpm)
- Change from baseline in binocular reading speed, as measured by IReST
- Change from baseline in FRI Index score at Month 24
- Change from baseline in VFQ-25 total score
- Incidence of CNV in the study eye, when the fellow eye has CNV at baseline

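### The SAP counts CNV in a study eye it neither defines nor freezes, while the protocol lets that eye be changed because it converted to CNV

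*Protocol*

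**What the plan says.** Protocol v1.1, section 1.12.1, has the PI and sponsor agree on a primary study eye and then leaves the choice open: "The choice of primary study eye may later be changed based on the totality of data collected during the study". The examples in brackets are "quality of imaging, conversion to CNV, reading center choice, etc". The one deadline is "but one eye must be selected prior to running efficacy analyses on atrophic lesions"; none is tied to the CNV analysis.

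Two guidelines follow, which the section says may be amended.

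- If only one eye meets the study-eye inclusion criteria, "that eye should be selected as the primary study eye".
- If both do, "the study eye shall be selected but the choice may be modified at the end of the study based on the following", followed by five grounds: lesion measurability, field of view, distance to the fovea, acuity and imaging.

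CNV incidence in the study eye is a secondary outcome measure in protocol 1.6.2, where the measure carries no fellow-eye restriction. SAP 2.2.3 restricts it: "Incidence of CNV in the study eye, when the fellow eye has CNV at baseline". SAP 6.3.5 analyses it by proportion per arm, difference in proportions and Fisher's exact test. SAP 2.2.5 and 6.4 add an exploratory version for fellow eyes with intermediate AMD.

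For GA area, LLVA and BCVA the SAP works with Eligible Eyes, defined in 6.1 by measurable GA and absence of CNV at baseline on central reading. It gives no definition of the study eye.

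**The concern.** The unit in which the event is counted may be changed because that unit had the event. If a converting study eye is re-designated as the fellow eye, its conversion leaves the numerator. In the SAP subset the subject may leave the denominator as well, since the new fellow eye had no CNV at baseline.

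Protocol 1.6.1 gives the SAP precedence where the two documents differ on endpoints and analyses. The SAP is silent on which eye is the study eye, so there is no discrepancy for that rule to resolve, and 1.12.1 stands. At stake is the completeness of a secondary endpoint that rests on very few events.

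**Working it through.** **Inputs.** Control CNV incidence is about 20% at 24 months when the fellow eye has CNV (protocol 1.5.8.2). A 75% reduction gives 0.20 × 0.25 = 5% on ALK-001. Protocol 1.15.1 gives 35% of subjects with fellow-eye CNV, 80% evaluable (stated for the primary outcome), and a one-sided Fisher test at 0.2. Allocation is 2:1 (protocol 1.7.1). SAP 3.1 reports 200 randomized instead of 300. The synopsis FAQ table gives 3-6% at 24 months when the fellow eye has GA.

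**Step 1: the plan's own figure.** 300 × 0.35 × 0.80 = 84 subjects, 28 placebo and 56 ALK-001. Exact power of the one-sided Fisher test at 0.2 for 20% versus 5% is 80.2%, which matches the stated 80%.

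**Step 2: events at N=200.** 200 × 0.35 = 70 subjects, about 23 placebo and 47 ALK-001. Expected events are 0.20 × 23 = 4.6 and 0.05 × 47 = 2.35, together 6.95, or about 7. On the protocol's criterion, power is 75.7% with all 70 and 63.4% with 56 evaluable (19 and 37).

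**Step 3: what lost events would do.** Suppose a fraction f of converting study eyes is re-designated to an event-free eye, equally in both arms. The documents give no value for f, so this shows only sensitivity.

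| f | Placebo | ALK-001 | Difference | Power, 28/56 | Power, 23/47 |
|---|---|---|---|---|---|
| 0 | 20% | 5% | 15 points | 80.2% | 75.7% |
| 0.25 | 15% | 3.75% | 11.25 points | 67.2% | 64.2% |
| 0.50 | 10% | 2.5% | 7.5 points | 49.5% | 46.4% |

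The ratio of rates stays at 0.25 throughout. The difference in proportions, which SAP 6.3.5 reports, shrinks toward zero. If the subject also leaves the denominator, f = 0.25 gives (4.6 − 1.15)/(23 − 1.15) = 15.8% and (2.35 − 0.59)/(47 − 0.59) = 3.8%, which is nearly the same.

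**Step 4: who can be switched.**

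- *Two eligible GA eyes.* Section 1.12.1 plainly applies. These subjects count under the protocol's unrestricted measure. An upper bound on their number at N=200 is everyone without fellow-eye CNV, 0.65 × 200 = 130. With no treatment effect that gives 130 × 0.03 = 3.9 to 130 × 0.06 = 7.8 conversions over both arms. The 130 include fellow eyes without GA, so the true figure is lower.
- *Fellow eye with CNV at baseline (SAP 2.2.3).* That eye meets study-eye exclusion 28, "Study eye has historical or active CNV", so normally only one eye qualifies and the single-eye guideline fixes it. Three narrow routes remain. Exclusion criteria can be waived on sponsor approval (1.8.2). Section 1.12.1 tests only the inclusion criteria, and inclusion criteria 9-15 do not mention CNV. Finally, PI and reading center may disagree on CNV: SAP 6.1.5.3 anticipates Eligible Eyes that the PI reported as having CNV, 6.3.5 does not say whose call defines fellow-eye CNV, and reading center choice is another named ground for a change.
- *Fellow eye with intermediate AMD and no GA (SAP 2.2.5).* That eye fails inclusion criterion 9 and cannot ordinarily become the study eye.

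**The case against.** The strongest reply is that the rule hardly reaches the SAP endpoint. A swap in that subset would mean choosing an eye that already had CNV. The synopsis requires a study eye free of current or past CNV, its FAQ table shows every study eye as pure GA, and exclusion 28 says the same. Sponsor exceptions are meant for matters without clinical or scientific significance (1.17.12). Leaving a newly converted eye for one with earlier CNV would also serve little purpose. This largely stands, and it is why exposure there is described as probably rare. It does not close the three routes above.

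It can also be said that the two-eye exposure sits under a protocol measure that the SAP has narrowed. That is right for the SAP tables. The exposure matters only if the protocol's broader measure is reported.

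A reader might infer that re-choice would remove placebo converters and so favour or disfavour one arm. The documents do not support that. Site staff and coordinating sponsor personnel are masked (protocol 1.9.7.1), and SAP 3.1 keeps staff who may be in contact with investigators or subjects masked until database lock. A reader might also take CNV to be one of the listed grounds for the end-of-study change in two-eye subjects. It is not; it appears in the general sentence before that list.

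**Conclusion.** The gap is real and small. The protocol permits an outcome-dependent change of study eye on a named ground that is itself the counted event, and the SAP does not neutralise it for the CNV endpoints. The expected consequence is lost events and lower power on an endpoint with about 7 expected events at N=200. How many would be lost cannot be estimated, because the documents give no switching rate. The figures rest on the protocol's 20% control rate, 75% reduction and 35% subset share. The power figures also use its one-sided 0.2 level, whereas SAP 6.0 makes efficacy tests two-sided.

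It would be wrong to conclude that the trial's main result is compromised. The primary, LLVA and BCVA analyses use Eligible Eyes set by baseline status, and re-designating the study eye does not alter them. CNV incidence is also outside the tested sequence in SAP 6.2.1. This is a free improvement to the SAP.

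**What to change.** In SAP 2.2.3, 2.2.5, 6.3.5 and 6.4, define study eye and fellow eye as those designated at or before randomization. State that every CNV conversion in that study eye is counted, and that any later re-designation under protocol 1.12.1 does not apply to the CNV endpoints.

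The cost is wording only. The v1.1 events table (protocol 1.2) already records the primary study eye at V01. Section 1.12.1 has both eyes undergo the study procedures, and the synopsis FAQ keeps subjects in the study after CNV develops in the study eye. No new data, visits or subjects are needed. Because SAP 3.1 reports randomization as completed, the change belongs in the SAP rather than in trial conduct.
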